Feasibility and acceptability of six-weeks of high intensity interval training in wheelchair users with SCI

Short Title: HIIT in Spinal Cord Injury (HIIT-SCI)

Principal Investigator: [name], RET
Human Engineering Research Laboratories
VA Pittsburgh HealthCare System
University of Pittsburgh
[name]
[name]
[contact]

Funded By: University of Alabama – Birmingham
[name]
[name]
[contact]

Eunice Kennedy Shriver National Institute of Child Health and
Human Development (NICHD)
NIH Clinical Center
[name]
[name]

Study Protocol Number: NCT03152110 (National Clinical Trials)
PRO17020277 (OSIRIS)
STUDY19040142 (University of Pittsburgh)

Overview

An upper extremity form of high intensity interval training (HIIT) that is effective, safe, quick and has acceptable positive affect could be an attractive option for persons with SCI who are not presently exercising and have low fitness levels. The study will look at feasibility and acceptability of a 6-week HIIT program for persons with a spinal cord injury/dysfunction who are untrained. Additionally, the study will look at the effects of the training program on changes in activity levels. Participants will complete a 6-week HIIT training program in their homes, as well as two laboratory visits where aerobic and anaerobic fitness will be measured.

Research Activities and Consent

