If the participant already owns a handcycle, we will make every attempt to fit their handcycle to the roller system that will be used for the study. If we are not able to retrofit their handcycle or if they do not own a handcycle, the study team will provide a handcycle for the duration of the program. If a participant is unable to transfer into the handcycle, then the study team will provide assistance and tips for how to get in and out. If a participant is still uncomfortable with transferring into the handcycle, then they may be provided with an add-on hand bike, or they have the option to not participate in the study. At the end of the study, the handcycle/hand bike and the roller system will be returned to the study team. Participants will be given a heart rate monitor, which they will be asked to wear and use for every exercise session for the duration of the study. They do not have to return the heart rate monitor at the end of the study. Participants will be provided with a bike computer that will be fit to the handcycle/hand bike and will be used solely for the purpose of recording power output and heart rate during the exercise sessions. Participants must return the bike computer at the end of the study.

The first exercise visit will be tentatively scheduled within one week of the first study visit. Exercise sessions will be scheduled, ideally, 3 times per week (every other weekday), with the total training protocol lasting 6 weeks. Two of the sessions will be supervised by a trainer and one session will be completed on their own. The trainer may go to the third session if the participant requests assistance getting in and out of the handcycle or attaching the add-on hand bike, however, they will not provide any coaching or verbal cues during exercise. During the last week (week 6), subjects can opt to have their supervised sessions via FaceTime or Skype (if they have a smartphone or computer). The exercise goal for all participants is to achieve 10 sets of 60 second bouts of arm cycling at 90% of their PPO (as determined in baseline testing), separated by 60 seconds of active recovery.

Further details regarding the supervised and unsupervised workouts are explained below.

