(A) Supervised exercise sessions: the trainer will meet the participant at their home for each supervised exercise session. Prior to exercise, the trainer will measure/record the participant's heart rate and blood pressure. In addition, the trainer will make sure that there haven't been any recent changes in health or medical status (please see "Exercise Training Intake Form" in the "Supporting Documentation" section).

The trainer will guide the participant through a warm-up and stretching routine prior to exercising (approximately 10 minutes). The participant will be familiarized with the same Borg and Wheel RPE scales used during Visit 1, and the Feeling Scale (please see "Feeling Scale" in the "Supporting Documentation" section). The Feeling Scale (-5 very bad to +5 very good) is commonly used to measure affective response during exercise.

The trainer will prescribe individualized work and rest phases based on their PPO from their maximal aerobic test. In order to reach the HIIT goal mentioned above, the trainer will hold participants at 90% PPO as a constant target intensity to start, shortening the work phase (e.g. 10-15 seconds), and if necessary, lengthening the recovery phase (e.g. 75-90 seconds). These ramping parameters will be progressed and documented by the trainer for each session. The trainer will determine when to change their work and rest parameters based off of heart rate and self-reported RPE.

At the end of each session, the trainer will measure/record the participant's heart rate and blood pressure again. Power output and heart rate data is automatically stored in the bike computer during each exercise session. After each session, the data will be transferred to a study iPad/laptop via USB and then deleted from the device. These measures are collected to evaluate adherence to the prescribed HIIT intensities.

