(B) Unsupervised exercise sessions: participants will be asked to repeat the same HIIT protocol they performed during the previous supervised session. The trainer will provide written directions for their convenience. Participants will be instructed to wear the heart rate monitor so that during the next supervised exercise session, the trainer will be able to retrieve/collect the data to store on one of our study devices for future analysis. The heart rate data as well as power output data will automatically be stored on the device in the same manner as during the supervised sessions. At the next supervised session, the trainer will retrieve the data from the device.

Visit 2

After completing the 6-week HIIT program, participants will be scheduled for a second/final lab visit. Visit 2 will be ideally scheduled within one week of finishing the 6-week HIIT program, but to provide scheduling flexibility, participants have up to two weeks to complete their second visit. We will try to schedule the follow-up exercise testing around the same time of day as Visit 1. Participants will complete the same exercise testing protocol that was completed in Visit 1. Participants will also complete the NRS, WUSPI, POMS and SF-36 WW questionnaires from Visit 1. Participants will be asked to complete a survey regarding their satisfaction of the HIIT program using the Physical Activity Enjoyment Scale (PACES). Participants will be provided with an open-ended questionnaire to discuss their feelings about HIIT, likelihood to continue, and what would be needed in terms of support to help them (or others like them) to keep doing HIIT. Activity monitors will be removed from the subject and wheelchair.

*Please note: some participants take longer than others to finish questionnaires; to decrease burden, participants will be allowed to complete the questionnaires over the duration of the first lab visit and the first home visit (for baseline measures) and last home visit and second lab visit (for post-trial measures).

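### PACES and the open-ended HIIT questionnaire may be completed at the last home visit, where the trainer may be present and training may be unfinished; this risks an upward bias of unknown size in acceptability

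*Protocol*

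**What the plan says.** The protocol's Overview states the purpose: "The study will look at feasibility and acceptability of a 6-week HIIT program" for untrained people with spinal cord injury or dysfunction. Both words are also in the title.

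The Visit 2 section lists two end-of-program forms that bear directly on acceptability. One is "a survey regarding their satisfaction of the HIIT program using the Physical Activity Enjoyment Scale (PACES"). The other is introduced as follows: "Participants will be provided with an open-ended questionnaire to discuss their feelings about HIIT". It also covers likelihood of continuing and the support that would be needed.

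A note at the end of that section, written to reduce burden on slow completers, says that "participants will be allowed to complete the questionnaires over the duration of" two visits at each end of the study. For the post-trial forms these are the "last home visit and second lab visit (for post-trial measures"). The note makes no exception for either form.

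On who is in the home, the subsection on supervised sessions says "the trainer will meet the participant at their home for each supervised exercise session". The introduction to the 6-Week HIIT Protocol adds two qualifications. In week 6, "subjects can opt to have their supervised sessions via FaceTime or Skype". At other times the trainer may attend the third, otherwise unsupervised, weekly session if the participant needs help with the equipment.

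The SAP does not name PACES or the open-ended form. They fall under its general provision for summary statistics on all variables.

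**The concern.** A participant asked how much they enjoyed a program, and whether they would carry on with it, may answer more kindly when the person who has been training them is in the room or will collect the form. The expected direction is upward, towards finding the program acceptable.

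Three features make such a shift hard to deal with afterwards. No comparison group is described. Neither form is among the eight baseline instruments, so there is no within-person reference. The plan does not say that place of completion will be recorded, so results could not be split by setting even descriptively.

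The same note leaves the timing loose. Visit 2 follows the end of training by definition, but the last home visit need not. Participants could be rating different amounts of the program.

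**Working it through.** The plan gives no PACES mean, standard deviation, acceptability threshold or expected share of home completers, so there is no figure to reproduce and no bias to compute. The check sets the provisions side by side, with simple counting for the timing.

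**1. Are the two forms covered by the note?** Yes. Both are listed under Visit 2, the note follows in the same section, and it refers to the questionnaires without exception.

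**2. Is the trainer likely to be at the last home visit?** During the program, the home visits described are supervised sessions, or third sessions where the trainer helps with equipment. The protocol assigns no other staff member to them. Equipment has to be returned at the end of the study, but no collection visit is described. An in-person last home visit is therefore most naturally read as a trainer visit. That is an inference; the protocol does not say that the trainer is present while forms are filled in.

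**3. Are the answers shielded from the trainer?** The available text does not say who hands out the forms, who collects them, or whether they are completed in private.

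**4. Can the last home visit precede the end of training?**
- Planned sessions: 3 per week × 6 weeks = 18, of which 2 × 6 = 12 are supervised and 1 × 6 = 6 are done alone.
- Week 6 in person, last session of the week supervised: 0 sessions remain at the last home visit.
- Week 6 in person, last session of the week done alone: 1 of 18 remains.
- Week 6 supervised by video, with no visit to help at the third session: the last in-person visit is in week 5, so at least 3 of 18 remain (3/18 = 16.7%). If the week 5 solo session is also still to come, 4 of 18 remain (4/18 = 22.2%).
- At the other end, Visit 2 may take place up to two weeks after the program finishes.

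In the video case, ratings could range from about one week before the end of training to two weeks after it, a spread of roughly 1 + 2 = 3 weeks. This assumes that a video session is not itself counted as a home visit, which the protocol leaves undefined.

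**5. Which results depend on these forms?** The SAP's primary outcome measures are peak power, peak VO2 and time to exhaustion. Its feasibility measures are sessions completed and sessions meeting the target intensity. None uses PACES or the open-ended form.

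**The case against.** A reader might infer that the trainer will be present and that acceptability will be biased upward. The documents do not support either as fact. Home completion is an option, both forms are primarily Visit 2 items, and week 6 supervision may be remote. Only a risk can be claimed.

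Several other strong readings also go too far:
- That one trainer coaches each participant throughout. The protocol does not say so.
- That the forms rate the trainer. They are described as concerning the program and HIIT, and the exercise goal is common to all participants, although the trainer sets individual progression.
- That acceptability is one of only two study questions. The activity-monitor section refers to a fifth aim.
- That speed of completion alone decides where the forms are filled in. The note gives slow completion as the reason for flexibility but sets no rule on which forms move.
- That the lab is a neutral setting. Nothing shows that Visit 2 staff are independent of the trainers, so moving the forms there does not by itself remove a courtesy effect.

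It can also be said that PACES has no threshold or test attached, so no stated decision would change. Handling instructions may also exist in the supporting documentation, the consent pages or the part of the SAP that was not available to read.

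These points limit the claim and shape the remedy. What they leave standing is that the note permits completion of both forms at a visit the trainer normally attends, and that the available text contains no safeguard.

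**Conclusion.** The point holds as a risk. The note allows the two forms that most directly measure end-of-program acceptability to be completed where the trainer may be present, and possibly before training has finished. The expected direction is upward and the size is unknown. It could affect only participants who use the home option for these forms, and how many will do so cannot be told from the documents.

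The consequence is confined to questionnaire-based acceptability. It does not touch the session counts, the target-intensity counts or the exercise tests. It still merits a change because acceptability is in the title, the single-group design cannot reveal the shift, and it cannot be repaired after the data are collected.

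The conclusion rests on two assumptions: that the last home visit is normally a trainer visit, and that no handling instruction elsewhere already separates the forms from the trainer. If such an instruction exists, the courtesy concern largely falls away, but the timing point remains.

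**What to change.** Amend the note at the end of the Visit 2 section along these lines:

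> PACES and the open-ended HIIT questionnaire are self-completed in private after the final training session, either at Visit 2 before exercise testing or at home. They are returned sealed or online to a member of staff other than the participant's trainer. The date and place of completion are recorded. The remaining post-trial questionnaires (NRS, WUSPI, POMS, SF-36 WW) may be completed over the last home visit and Visit 2.

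Privacy and the return route matter more than the venue, because the lab staff are not shown to be independent of the trainers. Requiring completion after the final session also settles the timing question. With date and place recorded, PACES can be summarised by setting as a descriptive check.

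The cost is small: a few extra minutes at Visit 2 for slow completers, some handling of returned forms, and no additional staff. Restricting the forms to Visit 2 alone would lose data from anyone who finishes training but misses that visit; the private-return option avoids this.

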## **Statistical Analysis Plan**

Distributions of all data will be examined. Should outliers or distributions that are nonlinear in nature be present, appropriate transformations will be performed. Means and standard deviations, or medians and ranges, as appropriate, will be calculated for all variables. Total number of training sessions completed and numbers of sessions meeting criteria for HIIT target intensity (e.g. average power achieved over work phases) will be determined to evaluate feasibility. A paired t-test will be used to compare the primary outcome measures obtained during the pre and post exercise max testing (i.e. physical capacity measures [peak power, peak  $\text{VO}_2^+$ , time to exhaustion]).

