(6) Physical Activity Stages of Change: This is a brief, 5-item, yes/no questionnaire that assesses an individual's readiness to exercise.

(7) Exercise Participation Evaluation: This is a 4-item questionnaire developed by our study team that will be used to determine if the participant exercises, and if so, what type of exercise and how frequent.

(8) Profile Of Mood States (POMS): This is a validated questionnaire that contains a series of descriptive words/statements that describes feelings. The participant will self-report on each of these areas using a 5-point Likert scale to assess total mood disturbance.

Lastly, height and weight will be taken. Subjects will transfer to a mat table where they will lay on their backs. Once in this position we will measure their height with a measuring tape. Weight will be measured using a wheelchair scale. Participants will be weighed with their wheelchair and the wheelchair will be weighed without the subjects in them. The weight will be the difference between the two measurements.

Following completion of all study questionnaires, participants will begin exercise testing. Both exercise tests will be administered by an exercise physiologist and directly supervised by a physician.

Both tests have been widely used in previous research studies. The tests are outlined in further detail below:

(1) Maximal aerobic exercise test: the purpose of this test is to evaluate cardiac function and fitness. Additionally, this test will determine peak power output (PPO) which will later be used to set an individualized goal for the participant during the HIIT protocol to be completed in the second, and possible third and fourth visits. Prior to starting the test, participants will be fitted with a mask that analyzes the air that is being inhaled and exhaled (also known as "open circuit spirometry"). Cardiorespiratory measures (i.e., heart rate, blood pressure, oxygen consumption, respiratory exchange ratio, pulmonary ventilation, carbon dioxide expiration, etc.) will be recorded throughout this test. A heart rate monitor will be worn around the chest. Participants will be able to use a private space to put on the heart rate monitor. A member of the study team will verify the heart rate monitor is placed properly.

Prior to beginning the test, the Borg and Wheel scales will be explained to participants (please see "Borg Scale" and "Wheel Scale" under the "Supporting Documentation" section). Ratings of

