Perceived Exertion (RPE) scales (such as the Borg and Wheel scales) rate how hard a person feels their body is working and is an accepted supplementary tool for exercise programs. Throughout the test, the participant will be asked to report their RPE by pointing to the corresponding number on the scale. The exercise test will be administered using an incremental, modified protocol on an electronically-braked arm ergometer. A study team member will choose one of two exercise protocols, depending on the answers to the questions on the demographics questionnaire.

For one protocol, the resistance will initially be set at 10W and will increase by 10W every minute until the participant can no longer continue, or until their respiratory exchange ratio exceeds 1.15. For the second protocol, the resistance will initially be set at 35W and will increase by 10W every minute until the participant can no longer continue, or until their respiratory exchange ratio exceeds 1.15. Both protocols will ask the participant to maintain an RPM of 55-65 revolutions per minute (RPM). If the RPMs drop below 55 for more than 20 seconds, the test will be completed.

(2) Maximum power output test: the primary purpose of this test is to evaluate the highest amount of power that the participant can produce in a short period of time. Other measures include heart rate, blood pressure, relative peak power, anaerobic capacity and anaerobic fatigue. The same ergometer will be used for this study that was used for the maximal aerobic exercise test. Initially, the resistance will be set at zero and will then be increased over the duration of the test. The actual test will last one minute in duration. For the first 30 seconds, the participant will crank on the cycle with minimal resistance. Then, the resistance will be increased to a maximal level and participants will crank as hard and as fast as they are able to for the last 30 seconds. After that the test is completed, the resistance will then return to zero and the participants will cycle at a comfortable pace to cool down.

Participants will rest a minimum of 20 minutes in between each assessment.

Following completion of the exercise tests, the study team will introduce the participant to the type of exercises that will be performed for the study. They will be able to use the ergometer in the lab to try out a brief HIIT protocol.

Activity Monitor Data Collection

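### Do three primary fitness measures with no lead, and feasibility counts with no interval, call for a change to the plan?

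*SAP*

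**What the plan says.** The protocol's Overview sets the purpose: "The study will look at feasibility and acceptability of a 6-week HIIT program for persons with a spinal cord injury/dysfunction who are untrained". The SAP's Statistical Analysis Plan section evaluates feasibility from the number of sessions completed and the number that met the target intensity. For description it says: "Means and standard deviations, or medians and ranges, as appropriate, will be calculated for all variables".

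For fitness it says: "A paired t-test will be used to compare the primary outcome measures obtained during the pre and post exercise max testing", and lists peak power, peak VO2 and time to exhaustion. In the text available it gives no order among the three, no alpha and no adjustment.

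The protocol describes two exercise tests at Visit 1.

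- **The maximal aerobic test** is a ramp and yields peak power output (PPO). In one form, "the resistance will initially be set at 10W and will increase by 10W every minute until the participant can no longer continue". In the other, "the resistance will initially be set at 35W and will increase by 10W every minute". Either form also ends if the respiratory exchange ratio exceeds 1.15 or if cadence stays below 55 RPM for more than 20 seconds.
- **The maximum power output test** is short: "The actual test will last one minute in duration". Relative peak power is among its measures.

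At Visit 2, "Participants will complete the same exercise testing protocol that was completed in Visit 1".

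**The concern.** Three things look wrong at first.

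1. Three measures are called primary and each is tested, with no rule for reading them together. If one significant result out of three were taken as success, the error rate would exceed the per-test level.
2. Two of the three may be nearly the same measurement. On a ramp of fixed slope, the load reached and the time taken are set by the same stopping moment. Improvement in both could be presented as two findings that support each other.
3. The study is about feasibility, yet its only planned hypothesis tests concern fitness, and the feasibility results carry no statement of precision.

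At stake would be an overstated fitness effect and an understated uncertainty about adherence.

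**Working it through.** The available text gives no sample size, alpha, SD of change or expected adherence, so there is no planned figure to reproduce. Assumptions: two-sided 0.05 per test; n = 10 or 20; SD of change in ramp time 0.5, 1 or 2 minutes; correlation of peak VO2 with each of the other two measures from 0 to 0.8; mean sessions 14 or 16 with SD 2 or 4. From the documents: slope 10 W per minute, starting load 10 W or 35 W, same testing at both visits, and 3 sessions × 6 weeks = 18 scheduled sessions.

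**Overlap of ramp power and time.** With starting load s and time t in minutes, pro-rated PPO = s + 10t. If the same ramp is used at both visits, s cancels:

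change in PPO = (s + 10·t_post) − (s + 10·t_pre) = 10 × change in t.

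The paired t statistic does not change when the data are multiplied by 10, so the two p-values are identical.

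If PPO is scored in whole 10 W stages, each visit adds a rounding error with variance of about 1/12 in stage units, so the change carries about 2/12 = 1/6. Then r ≈ SD / √(SD² + 1/6):

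- SD 0.5: √(0.25/0.4167) = 0.775
- SD 1: √(1/1.1667) = 0.926
- SD 2: √(4/4.1667) = 0.980

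Simulation gives the same values. At SD 0.5 the shared variance is 0.775² = 60%, which is well short of one result.

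**Error across three tests.** Under independence, 1 − 0.95³ = 14.3%. If ramp power and time are identical and VO2 is independent, 1 − 0.95² = 9.75%. Simulated under the null (200,000 replicates, range over n = 10 and 20 and over the VO2 correlations):

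| r (power, time) | At least one false positive | Time also significant when power is a false positive |
|---|---|---|
| 0.78 | 10.1-12.7% | 36-39% |
| 0.93 | 9.2-11.6% | 62-65% |
| 0.98 | 8.7-10.7% | 79-81% |
| about 1 | 7.9-9.9% | 98-99% |

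The first two worries pull against each other: the closer the duplication, the smaller the inflation. A reader who wants strict control can compare the reported p-values with 0.05/3. Under independence that gives 1 − (1 − 0.05/3)³ = 4.9%, and with the overlap about 3-4%. Nothing needed for that reading is lost under the plan as written.

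**Precision of the session counts.** A reader given mean, SD and n can form mean ± t × SD/√n. The half-width is 0.72 SD at n = 10 and 0.47 SD at n = 20. Sessions were simulated as beta-binomial out of 18 (40,000 trials; n = 10 / n = 20):

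| Mean, SD | t-interval coverage | Upper limit above 18 | Logit-scale coverage |
|---|---|---|---|
| 14, 2 | 94.6 / 94.9% | 0 / 0% | 95.3 / 95.2% |
| 14, 4 | 92.4 / 93.3% | 6.7 / 0% | 95.1 / 95.0% |
| 16, 2 | 92.4 / 93.3% | 6.8 / 0% | 94.9 / 94.9% |
| 16, 4 | 81.3 / 88.6% | 86.2 / 35.1% | 89.2 / 93.0% |

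Only the last row is poor. It corresponds to beta parameters 1.0 and 0.125 (mean 18 × 1/1.125 = 16), with about 65% of participants at exactly 18. For data of that shape the SAP's own choice of median and range applies, and the logit-scale interval also falls short at n = 10.

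**The case for a change.** The best case for a change is that the facts are right and the remedy is cheap. The SAP does call three measures primary, and they are the only ones given a hypothesis test. Listing peak power beside peak VO2 and time to exhaustion points to the ramp. Time to exhaustion cannot come from a test of fixed length, and the protocol ties PPO to the ramp. The other stopping rules end both measures at the same moment, so they do not break the link. A few sentences would name a lead, identify the test and add intervals.

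What stands is that the SAP does not say which test supplies peak power. If it is the ramp, improvement in power and in time should be read together and not as independent support.

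What does not stand is the step from there to a defect. Without the word output, peak power appears in the protocol only as relative peak power under the one-minute test. If that test is the source, the duplication falls away and only the 14.3% ceiling remains. If the ramp is the source, the strength of the overlap rests on a scoring rule and an SD of change that the documents do not give. The multiplicity harm needs a rule that any one significant result means success, and none is visible. Which measure should lead in a small single-arm study of this kind is open to debate. Choosing one without sight of the numbered aims, to which the protocol's activity-monitor section alludes, would be a preference.

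**Conclusion.** No change follows. Each paired comparison is valid at its own level, and all three are named beforehand. Reporting all three leaves little room for selection. The familywise figure of about 8-13% (ceiling 14.3%) describes a decision rule that the plan does not adopt. Ramp power and time may duplicate each other, with r about 0.78 to 1 depending on scoring and on an assumed SD of change of 0.5 to 2 minutes. That is a matter for interpretation when results are written up, and it disappears if peak power comes from the one-minute test. Confidence intervals for paired changes and for sessions per participant are ordinary reporting additions that use data already collected. The ordinary t interval covers 92.4-94.9% in three of the four assumed settings, and the fourth is one where the plan already allows median and range.

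This rests on assumed values for n, alpha, SDs, means and correlations. One part of the SAP was not available, so it cannot be shown that a lead measure, an alpha or a hierarchy of aims is absent from the plan as a whole.
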